7.12 Safety Analyses

The safety analyses will be presented by the treatment period for the Safety Analysis population.

7.12.1 Adverse Events

All AEs will be coded using the most current version of MedDRA. TEAEs and SAEs will be summarized descriptively for each treatment period.

A treatment emergent adverse event (TEAE) phase is defined as meeting either of the following 2 criteria:

- Any AE that has an onset on or after the index injection and within (after) 30 days of the last study treatment.
- Any pre-existing AE that has worsened in severity on or after the index injection and within (after) + 30 days of the last injection.

TEAEs for each treatment period, will be assessed as follows:

- A TEAE will be assigned to the treatment received immediately before onset.
- If the severity of a TEAE increases in a later period the TEAE at the increased severity will be assigned to the treatment received immediately before the increase in severity.

Onset date of adverse events on or post visit 3 but before visit 11 were considered as occurring during T1; otherwise onset date of adverse events on or post visit 11 were considered as occurring during T2

A treatment-related AE is defined as an AE as being possibly, probably or related to the study drug. If an AE has missing relationship it is assumed to be related to the study drug for analysis purposes.

Severity is classified as mild/moderate/severe/life-threatening/death (last two grades applied for SAE). If a subject reports AEs more than once within a SOC/PT, the AE with the worst-case severity will be used in the corresponding severity summaries. TEAE summary tables (except the overall summary table) will be presented by severity and overall.

The following tables will be presented by severity and overall for AEs:

- Overall incidence and the number of AEs, SAEs, TEAEs leading to withdrawal.
- Treatment-Emergent Adverse Event by System Organ Class and Preferred Term
- Related Treatment-Emergent Adverse Event by System Organ Class and Preferred Term
- Serious Treatment-Emergent Adverse Events by System Organ Class and Preferred Term
- Serious Treatment Related Treatment-Emergent Adverse Events by System Organ Class and Preferred Term
- Treatment Discontinued Treatment-Emergent Adverse Events by System Organ Class and Preferred Term
- Summary of Treatment-Emergent Adverse Events Leading to Death

All AEs will be listed.

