2.2 Secondary Objectives

The secondary objectives of the study are to:

- Evaluate the safety and tolerability of single and repeat dose SP-102 (10 mg dexamethasone) administered by epidural injection in subjects with lumbosacral radiculopathy.
- Evaluate the analgesic effect on leg pain (as measured by the Numeric Pain Rating Scale [NPRS] in the affected leg) following the index (Treatment [T] 1) and repeat (T2) injections.

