3.4.2 Dosage Schedule

The subjects will receive 2 single epidural injection of SP-102 (10 mg in 2 mL) separated by 4 to 8 weeks. The IP will be administered by the Investigator. Specific instructions for IP administration are found in [Appendix D](#).

[figure not shown]

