3.5.2.8 Telephone Contact

The subject is to be contacted by telephone weekly to determine the need for the repeat injection (T2). If after 4 weeks from Visit 10, the subject does not need T2, schedule Visit 19/EOS/ET.

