3.5.5.5 Laboratory Parameters

The following clinical laboratory tests are to be performed at Screening, Baseline, T1 – Day 5, T1 – Day 28, T2 – Day 5, and T2 – Day 28 (Visit 19/EOS/ET) unless noted below:

Hematology: Hemoglobin, hematocrit, red blood cell count, WBC count (with differential [lymphocytes, neutrophils, eosinophils, basophils, and monocytes]), and platelet count.

Serum Chemistry: albumin, alkaline phosphatase, AST, ALT, direct bilirubin, total bilirubin, blood urea nitrogen, calcium, chloride, creatine kinase (Screening only), creatinine, gamma-glutamyl transferase, glucose, lactate dehydrogenase, potassium, sodium, and uric acid.

Other tests: HbA1c, HIV, hepatitis B, and hepatitis C at Screening. Coagulation tests at Screening or Baseline: activated PTT, PT, and INR. Coagulation tests may be repeated prior to the index and repeat injection, if deemed necessary by the Investigator.

Urinalysis: Dipstick analysis: color, turbidity, specific gravity, pH, glucose, protein, ketones, urobilinogen, bilirubin, blood nitrate, leukocyte esterase, and microscopic examination when indicated by dipstick results.

Urine drug screen: Includes opiates, barbiturates, benzodiazepines, tricyclic antidepressants, cannabinoids, PCP, cocaine, ecstasy, and amphetamines. A urine drug screen will be obtained at Screening, Baseline, and T1 – Day 28. A urine drug screen may be repeated if deemed necessary by the Investigator.

WOCBP: Serum pregnancy test at Screening. Urine pregnancy test at Baseline and at Visit 11 (T2 – Day 0). A urine pregnancy test may be repeated if deemed necessary by the Investigator.

Laboratory samples will be analyzed by the local laboratory. In the event of an unexplained clinically noteworthy abnormal laboratory test value, the test should be repeated immediately and followed up until it has returned to the normal range and/or an adequate explanation of the abnormality is found.

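### The by-treatment adverse-event tables set a 28 to 56 day T1 window beside a T2 window of about 30 days, so T1 gathers more background events whenever the gap exceeds about 30 to 33 days

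*SAP*

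**What the plan says.** SAP 7.12.1 (Adverse Events) defines a treatment-emergent event (TEAE) as "Any AE that has an onset on or after the index injection and within (after) 30 days of the last study treatment", or a pre-existing event that worsens in that span. For the by-period tables it then gives two boundary rules:

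- "A TEAE will be assigned to the treatment received immediately before onset".
- "Onset date of adverse events on or post visit 3 but before visit 11 were considered as occurring during T1", and "otherwise onset date of adverse events on or post visit 11 were considered as occurring during T2".

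Visit 11 is the T2 baseline visit, Day 0, on the day before the second injection (Protocol 3.1). Protocol 3.5.5.5 confirms the label: "Urine pregnancy test at Baseline and at Visit 11 (T2 – Day 0").

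On spacing, Protocol 3.4.2 says: "The subjects will receive 2 single epidural injection of SP-102 (10 mg in 2 mL) separated by 4 to 8 weeks". Protocol 3.5.2.8 sets the end of the wait: "If after 4 weeks from Visit 10, the subject does not need T2, schedule Visit 19/EOS/ET".

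SAP 7.3 shows adverse events by treatment and overall, with percentages based on observations or on the subject population. Neither document plans a common window or a person-time rate for adverse events. The related secondary objective (Protocol 2.2) begins: "Evaluate the safety and tolerability of single and repeat dose SP-102 (10 mg dexamethasone").

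**The concern.** The T1 column has no fixed end for a subject who is re-injected; it runs until the second injection. The T2 column ends about 30 days after that injection. If events occur at the same steady rate after both injections, the column with more days shows more subjects with events.

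The rule is also uneven inside the T1 column. An event in Week 7 after the index injection is a T1 TEAE if the subject later receives T2. In a subject who never receives T2, the index injection is the last treatment and the same event falls outside the 30-day limit. Classification therefore depends on a later clinical decision.

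Attribution adds to this. Protocol 4.1.5 treats temporal association as enough for a plausible link in analysis, and SAP 7.12.1 counts a missing relationship as related. Late background events can therefore be reported against the first injection.

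Elsewhere the plan matches its periods. The pharmacodynamic parameters use 28 days in each period (SAP 7.4.1, 7.4.2), and laboratory and vital-sign tables use matching post-injection days (SAP 7.12.2, 7.12.3). At stake is how a reader interprets the safety of the repeat injection.

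**Working it through.** **Longest T1 period.** The stated maximum participation is 15 weeks (Protocol 3.2). Screening of 21 days (3 weeks) + gap of 8 weeks + T2 follow-up of 4 weeks = 15 weeks, an exact match. If the 4 to 8 weeks began only after the T1 follow-up, the sum would be 3 + 4 + 8 + 4 = 19 weeks, which does not match. The T1 period is therefore G = 28 to 56 days.

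**Windows for a two-injection subject.**
- First rule, elapsed days: T1 = G, T2 = 30, ratio = G/30.
- Visit 11 rule, calendar days: T1 = G − 1, and T2 = 32 (the day before injection, the injection day and 30 days after), ratio = (G − 1)/32.

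**Incidence.** The documents give no adverse-event rate. Assumption: a constant hazard, equal after both injections, with 30-day subject incidence p. T1 incidence over G days is then 1 − (1 − p)^(G/30), and T2 incidence is p.

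| Gap G (days) | G/30 | (G − 1)/32 | T1 incidence, p = 20% | T1 incidence, p = 30% |
|---|---|---|---|---|
| 28 | 0.93 | 0.84 | 18.8% | 28.3% |
| 30 | 1.00 | 0.91 | 20.0% | 30.0% |
| 33 | 1.10 | 1.00 | 21.8% | 32.5% |
| 42 | 1.40 | 1.28 | 26.8% | 39.3% |
| 56 | 1.87 | 1.72 | 34.1% | 48.6% |

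For example, at p = 30% and G = 56, 1 − 0.70^(56/30) = 0.486. The break-even gap is 30 days under the first rule and 33 under the second. With 12 subjects, p = 20% and G = 56, about 12 × 0.341 = 4.1 subjects would have an event in T1 against 12 × 0.20 = 2.4 in T2.

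**How often T1 is the longer window.** Assumption: gaps spread evenly over the 29 whole-day values from 28 to 56. T1 is longer for 26/29 = 90% of gaps under the first rule and 23/29 = 79% under the Visit 11 rule. The mean gap is 42 days, a ratio of 1.40.

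**Dilution by T1-only subjects.** Assumption: 12 two-injection subjects, all with an 8-week gap, and 6 T1-only subjects. At p = 30%, T1 incidence = (12 × 0.486 + 6 × 0.30)/18 = 7.63/18 = 42%. The mean T1 window is (12 × 56 + 6 × 30)/18 = 47 days.

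**Sensitivity to the shape of the hazard.** If onset times decay exponentially with mean τ days after each injection, the ratio of events in 56 days to events in 30 days is (1 − e^(−56/τ))/(1 − e^(−30/τ)). This gives 1.01 for τ = 7, 1.11 for τ = 14 and 1.34 for τ = 30.

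**With one common window after each injection**, the expected T1 to T2 ratio at an unchanged constant rate is 1.00 for every gap.

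**The case against.** The strongest reply has four parts.

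1. *Direction.* A reader might infer that the rule always favours the repeat injection. The documents do not support that. At a 28-day gap the T2 window is slightly the longer one, and T1-only subjects have a T1 window of only 30 days. This stands.

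2. *No planned comparison.* A reader might also infer that a formal safety contrast of single versus repeat dose is biased. The objective reads single and repeat, adverse events are summarized descriptively, and no T1 to T2 test of them is planned. No error rate is affected. This stands, but the columns sit side by side and invite comparison.

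3. *Size.* The larger figures need a constant hazard and long gaps for every subject. Events close to the injection are almost unaffected. This stands; the distortion concerns background and late events.

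4. *Mitigation.* All adverse events are listed (SAP 7.12.1), with study day counted from each period's injection (SAP 7.2.1). With about 12 re-injected subjects, late T1 onsets can be found one by one. This limits the harm but does not correct the tables.

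Equal windows would also not make the columns fully comparable, because T2 subjects are selected. An adverse event of special interest bars re-injection (Protocol 3.3.3), and T2 requires the investigator's decision (Protocol 3.3.1.2).

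**Conclusion.** The concern holds with limits. The windows are unequal by rule, and nothing in the plan adjusts for it. For gaps longer than about 30 to 33 days, T1 is inflated relative to T2; at 28 days the effect is neutral to slightly reversed. Under a constant, equal hazard the time-at-risk ratio is 1.40 at 6 weeks and 1.87 at 8 weeks for two-injection subjects, with dilution from T1-only subjects. With early clustering (mean 7 days) it is about 1.01. The actual size depends on gaps and event timing that are unknown in advance, which is the reason to fix the window beforehand.

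This is a matter of presentation and interpretation in a secondary, descriptive analysis. It is worth correcting because the correction is cheap. Separately, the Visit 11 sentence assigns events on the day before the second injection to T2, while the other rule assigns them to T1. The effect is about one day, but the two cannot both be applied.

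**What to change.** In SAP 7.12.1, for the by-treatment adverse-event tables:

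- Count TEAEs with onset from the injection (Day 1) through Day 28 of each period. By the SAP 7.2.1 day count, a second injection 28 days after the first falls on T1 Day 29, so the window fits even the shortest gap.
- Use subjects dosed in that period as the denominator. SAP 7.3 leaves this open.
- Show later TEAEs in a separate column, labelled as after Day 28, for both T1 (up to the T2 injection) and T2. State that these two columns cover unequal time and are not for comparison.
- Leave the Overall column unrestricted, so every TEAE now tabulated stays tabulated.
- Reconcile the Visit 11 boundary with the rule based on the treatment received immediately before onset.

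The cost is SAP wording and one extra column per period, with no new data. The downside is that events after Day 28 leave the comparison columns, though they remain visible. A common window does not remove the selection of who receives T2; a table footnote should say so.

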3 INVESTIGATIONAL PLAN

3.1 Overall Study Design and Plan

[figure not shown]
This is an open-label, single-arm, repeat dose study to characterize the PD and safety/tolerability of SP-102 (10 mg dexamethasone) administered by TF or IL injection under fluoroscopic guidance in subjects with lumbosacral radiculopathy.

Subjects meeting the eligibility criteria will be enrolled in the study and receive a single 2-mL epidural injection of SP-102 (10 mg dexamethasone) in T1 (index injection) and T2 (repeat injection), separated by 4 to 8 weeks. T2 will only be provided if a repeat injection is warranted and the subject continues to meet applicable study inclusion and exclusion criteria.

Subjects who have been using opioids other than high dose opioids within 30 days prior to Screening (see Exclusion #12), may participate in the study if they agree to discontinue the opioid therapy prior to the Screening Visit and sign the pre-screening informed consent form (ICF).

The study will include a 21-day screening period (Visit 1), sequential treatments periods T1 and T2, separated by 4 to 8 weeks; each treatment period will consist of a Baseline Visit (Day 0), SP-102 injection (Day 1), and a 4-week follow-up period. Screening, Baseline, and follow-up visits will occur at the research site. Subjects will stay in a restricted environment (██████████) for each of 5 nights beginning the night before each injection to ensure fasting each evening and on-time collection of PD assessments each morning. Subjects will be permitted to leave the restricted environment (██████████) and resume normal activities each day after study procedures are performed. The SP-102 injection will be administered in an injection procedure facility. Safety and PD assessments will be collected at Screening, pre-dose, daily for 4 days post dose during the stay in the restricted environment (██████████), and at 3 outpatient follow-up visits (on Day 8, Day 15, and Day 28) after each injection. The end of study (EOS) visit (Visit 19) is the final outpatient visit after the second injection. If the subject is not eligible for T2 or chooses to withdraw from further participation in the study, the subject will be scheduled for the EOS visit (Visit 19).

Figure 3.1 Study Schematic

Abbreviations: EOS=End of Study; T = treatment

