3.5.2.4.1 Visit 3 (Treatment 1 – Day 1, Day of SP-102 Injection)

[REDACTED]

[REDACTED]

[REDACTED]

[REDACTED]

3.5.2.4.2 Visit 4 through Visit 7 – Days 2, 3, 4, and 5

[REDACTED]

[Redacted text block]

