3.5.2.9 Visit 11 (Treatment 2 Baseline)

[REDACTED]

[Redacted text block]

[Redacted text block]

[Redacted text block]

3.5.2.10 Treatment 2

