3.5.2.10.1 Visit 12 (Treatment 2 – Day 1, Day of SP-102 Injection)

[Redacted text block]

[REDACTED]

3.5.2.10.2 Visit 13 through Visit 16 – Days 2, 3, 4, and 5

[REDACTED]

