7.10 Prior and Concomitant Medications

Prior medications are defined as all medications starting and ending before the first dose of study drug. Prior medications will be summarized for all subjects. Concomitant medications are defined as medications taken on or after the date of the index injection through the EOS/ET participation. Concomitant medications will be summarized by treatment period (T1/T2) using ATC Level 2 and listed. If the onset date of a concomitant medication is on or post the index injection dosing date but before the repeat injection dosing date, it will be considered as occurring during T1; otherwise,

the onset date of concomitant medication on or post the repeat injection date will be considered as occurring in T2. If a medication is taken during both treatment periods it will be counted in both periods.

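### SAP 7.12.1 opens the T2 adverse-event period at Visit 11, before the repeat injection at Visit 12, and so conflicts with its own rule for assigning TEAEs

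*SAP*

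**What the plan says.** SAP 7.12.1 first states a rule based on treatment: "A TEAE will be assigned to the treatment received immediately before onset". It then states a rule based on visits. For the index period: "Onset date of adverse events on or post visit 3 but before visit 11 were considered as occurring during T1". For the repeat period: "otherwise onset date of adverse events on or post visit 11 were considered as occurring during T2". It does not say which rule prevails.

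The visit numbers are fixed by the protocol. The heading of Protocol 3.5.2.9 begins "Visit 11 (Treatment 2 Baseline", and that of Protocol 3.5.2.10.1 begins "Visit 12 (Treatment 2 – Day 1, Day of SP-102 Injection". SAP 7.12.2 labels Visit 11 as T2 Day 0. Visit 3 is the index injection day (Protocol 3.5.2.4.1).

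Two other places matter. Protocol 3.1 says that "each treatment period will consist of a Baseline Visit (Day 0), SP-102 injection (Day 1), and a 4-week follow-up period". SAP 7.10, on concomitant medications, uses the injection date as the boundary: an onset "on or post the repeat injection date will be considered as occurring in T2".

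**The concern.** On the Visit 11 date only the index injection has been given. The treatment-based rule puts an event starting that day in T1, and the visit-based rule puts it in T2. No reading satisfies both.

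Safety and tolerability of single and repeat dosing is a secondary objective, and TEAEs are tabulated by treatment period. With two boundaries in one section, two programmers could produce different T1 and T2 counts from the same data, and the T2 column could contain events that began before the repeat dose. With 12 re-injected subjects, moving one subject changes a T2 incidence by 1/12, about 8 percentage points.

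The visit rule also does not require that the repeat injection was given. T2 is conditional, so a subject may attend Visit 11 and not be re-injected. Some of that subject's TEAEs could then be labelled with a treatment never received.

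**Working it through.** The plan gives no figure to reproduce here. The check is to apply both rules to the same dates.

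**Inputs.** The injections are 4 to 8 weeks apart, i.e. 28 to 56 days (Protocol 3.4.2). Twelve subjects are to complete both injections (SAP 5). The TEAE limit is 30 days after the last injection (SAP 7.12.1). Visit 11 is taken as one day before Visit 12, from the Day 0 and Day 1 labels.

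**Notation.** The index injection is on date 0, the repeat injection on date g (28 to 56), Visit 11 on date g − 1, and AE onset on date d.

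| Rule | T1 | T2 |
|---|---|---|
| Last treatment received | 0 ≤ d < g | d ≥ g |
| Visit cut | 0 ≤ d < g − 1 | d ≥ g − 1 |

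The rules differ only at d = g − 1: date 27 for g = 28, date 41 for g = 42 and date 55 for g = 56. That is one onset day per re-injected subject, or 12 subject-days in all. It is 1/28 = 3.6% to 1/56 = 1.8% of the interval between injections.

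**Expected number affected.** The documents give no AE rate. Assume a constant rate with probability p of an AE per 30 days. The one-day probability is q = 1 − (1 − p)^(1/30). The chance that at least one of 12 subjects is affected is 1 − (1 − p)^(12/30).

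| p per 30 days (assumed) | q | 12 × q | At least one of 12 |
|---|---|---|---|
| 10% | 0.35% | 0.04 | 4% |
| 20% | 0.74% | 0.09 | 9% |
| 30% | 1.18% | 0.14 | 13% |

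**Sensitivity to the assumed rate and its timing.**
- A higher rate raises these figures. At an assumed 2% per day, which is 1 − 0.98^30 = 45% per 30 days, the chance of at least one is 1 − 0.98^12 = 22%.
- Clustering of events soon after injection lowers them. Assume a hazard half-life of 7 days, scaled to 20% at 30 days: cumulative hazard H × (1 − 2^(−t/7)), with H = −ln(0.8)/(1 − 2^(−30/7)) = 0.235. The hazard on the Visit 11 date is 0.235 × (2^(−27/7) − 2^(−28/7)) = 0.15% at g = 28, and about 0.01% at g = 56.

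**Subjects not re-injected.** The last dose is then the index injection, so TEAEs end at date 30. The earliest Visit 11 is date 27. A TEAE can be labelled T2 only if Visit 11 falls on dates 27 to 30, which gives at most 4 dates (27, 28, 29, 30). For a planned gap of 32 days or more, Visit 11 falls on date 31 or later and no TEAE is affected.

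**After the correction.** With T2 starting at date g, the two rules agree on every onset date for gaps of 28, 42 and 56 days.

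**The case against.** The best defence of the text is that Protocol 3.1 includes Day 0 in each treatment period, so a cut at Visit 11 follows the protocol's own definition of the T2 period. A reader might answer that T1 opens at its injection visit and not at its own Day 0, so the T2 cut must be a slip. That inference is not secure. T1 cannot open earlier, because a TEAE needs onset on or after the index injection, and Protocol 4.2.1 sends events before the first dose to medical history. The defence therefore explains the wording. It does not remove the conflict with the assignment rule, which refers to treatment received and not to period.

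Three stronger readings are tempting, and the documents do not support them.

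- **That SAP 7.2.1 contradicts the cut outright by making the event Day −1 of T2.** The negative-day formula there is tied to the index injection. No negative day relative to the repeat injection is defined, and counting days during T2 presupposes a definition of T2.
- **That SAP 7.10 shows a second error.** It governs medications only. A different boundary for another data type is a mismatch of convention.
- **That all later events in a subject not re-injected go to T2.** The 30-day limit confines this to a Visit 11 within 30 days of the index injection.

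It is also fair to say that the information needed for re-attribution will exist. SAP 7.3 provides an overall AE column, SAP 7.12.1 lists all AEs, and SAP 7.2.1 puts study day in every listing with an event date. This limits the harm but does not settle which rule the tables follow.

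**Conclusion.** The contradiction within SAP 7.12.1 is real, and no other section resolves it. It is minor.

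For re-injected subjects it concerns about one onset day each. Under the assumed constant rates of 10 to 30% per 30 days, the most likely outcome is that no subject is affected (87 to 96%). The one-day figure rests on the Day 0/Day 1 labels. The Visit 11 procedures and the schedule tables are redacted, so any visit window cannot be checked, and a longer gap between Visits 11 and 12 would widen the affected period. The number of subjects who attend Visit 11 without re-injection is unknown.

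A reader might go further and infer that the safety comparison of T1 with T2 is materially biased. The documents do not support that: attribution by period changes at the margin, while overall counts and listings are unaffected. Unequal lengths of the two periods, and the differing protocol statements on when AE recording ends (3.5.5.6 and 4.2.1), are separate matters and not part of this point.

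**What to change.** In SAP 7.12.1, replace Visit 11 with the repeat injection date (Visit 12) in both halves of the visit rule. Onset from the index injection date up to the day before the repeat injection date is T1, and onset on or after the repeat injection date is T2. State that T2 applies only to subjects who received the repeat injection, so that all TEAEs in other subjects stay in T1.

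The boundary should be a date and not a time, because Protocol 4 lists AE start and end dates but no onset time. Onsets on the injection date count as T2, in line with the SAP 7.2 convention that AEs starting on the reference start date are post-reference. An event that starts on the injection date but before the injection will still fall in T2, just as such an event on the index date falls in T1. The new boundary also matches the medication convention in SAP 7.10.

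The cost is one wording change and trivial programming, with no new data.
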